7.2.7. Clinical Laboratory Assessments

Clinical laboratory tests that will be performed in this study are presented in Table 6. In the event of an unexplained clinically relevant abnormal laboratory test occurring after study drug administration, the test should be repeated and followed up at the discretion of the investigator until it has returned to the normal range or stabilized, and/or a diagnosis is made to adequately explain the abnormality.

Table 6. Clinical Laboratory Tests

Hematology	
• Complete blood count with differential	
Chemistry	
• Albumin	• Creatinine clearance
• Blood urea nitrogen (BUN)	• Gamma glutamyl transferase (GGT)
• Calcium	• Glucose
• Carbon dioxide/bicarbonate	• Lactate dehydrogenase (LDH)
• Chloride	• Potassium
• Creatine kinase ^a	• Sodium
• Creatinine	• Uric acid
Liver Function Tests	
• Alkaline phosphatase (ALP)	• AST
• ALT	• Bilirubin (total and direct)
Coagulation Parameters	
• International normalized ratio (INR) time	• Prothrombin
Urinalysis	
• Bilirubin	• Proteins
• Glucose	• Red blood cells (RBCs)
• Ketones	• Screen for drugs of abuse
• Leukocytes	• Specific gravity
• Microscopy (if clinically indicated)	• Urobilinogen
• Nitrite	• Visual inspection for appearance and color
• pH	
Pregnancy Testing	
• Beta-human chorionic gonadotropin (WOCBP only)	• Urine pregnancy test
Serology	
• Hepatitis B, C, and Delta	• Human immunodeficiency virus I and II

^a Only required if ALT and/or AST is elevated 2 × higher than predose Day 1 baseline value

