- Repeat/unscheduled assessments: Only values collected at scheduled study visits/time points will be presented in summary tables. If a repeat assessment was performed, the result from the original assessment will be presented as the result at the specific visit/time point. All collected data will be included in the data listings. Unscheduled assessments intended as a re-test to replace missing values for scheduled visit will be used as if the results were taken on the scheduled visit for the purpose of summary table reporting.
- Assessment windows: All assessments will be included in the data listings and no visit windows will be applied to exclude assessments that were performed outside of the protocol specified procedure windows.
- Result display convention: Results will be center aligned in all summary tables and listings. Subject identifiers visit and parameter labels may be left-aligned if required.

- Date and time display conventions: The following display conventions will be applied in all outputs where dates and/or times are displayed:
 - Date only: YYYY-MM-DD
 - Date and time: YYYY-MM-DD HH:MM

If only partial information is available, unknown components of the date or time will be presented as 'NK' (not known), i.e., '2016-NK-NK'. Times will be reported in military time.

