12.2.1 Biostatistical Methods

All laboratory data collected at scheduled and unscheduled visits will be included in the listings, but only results collected as scheduled visits will be included in the summary tables.

Results for individual parameters may be reported in different units depending on the analyzing laboratory. If required, the results (and the corresponding normal range cut-off values) for individual parameters may be converted to International System of Units (S.I.) units to summarize the data.

For all the parameters where a unit value has been reported, the parameter names that will be used in the outputs will comprise of the test name and the unit of measure, for example, 'Albumin (g/L)'. Parameters will be sorted alphabetically within tables and listings.

For all parameters where a normal range limit value is reported, the normal range will be derived based on the available lower and upper limit values and any reported mathematical symbols. If both a lower and upper limit value is available, the normal range will be presented as '(Lower, Upper)'.

The reported results for each parameter with a defined normal range will be classified ('Low', 'or 'High') in relation to the defined normal range limits. If a result is equal to the normal range cut-off value, the result will be considered normal.

The change from baseline values at each post-baseline visit will be calculated for all parameters with continuous results.

The decimal precision to which the summaries for each parameter will be based on the maximum number of decimals to which the reported result or the normal range limits are presented to in the raw data. The results and normal ranges will be displayed to the same decimal precision in the listings.

The hematology and chemistry results tables will present summary statistics for each laboratory parameter within the specific test panel. For each parameter, summaries will be presented for the baseline and each scheduled post-baseline visit. In addition, summaries will be presented for the change from baseline values at each scheduled post-baseline visit.

Additionally, shift tables from baseline in CTCAE grade (version 5) from baseline will be summarized by counts and percentages along with a summary of maximum CTCAE Grade for post treatment lab assessments. The summary for the maximum CTCAE will be based on both scheduled and unscheduled visits.

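### No laboratory summary table specified in the SAP sets the worst CTCAE grade over all visits against the baseline grade

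*SAP*

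**What the plan says.** SAP 12.2.1 lists all laboratory data, "but only results collected as scheduled visits will be included in the summary tables". SAP 3.1 has the same general rule: "Only values collected at scheduled study visits/time points will be presented in summary tables". It adds that where a test was repeated, the original result is the one shown. Its one exception is a re-test that fills a gap at a planned visit: "Unscheduled assessments intended as a re-test to replace missing values for scheduled visit will be used as if the results were taken on the scheduled" (the quote stops just short of the end of that clause).

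SAP 12.2.1 then adds two graded displays. The first is that "shift tables from baseline in CTCAE grade (version 5) from baseline will be summarized by counts and percentages". The second comes "along with a summary of maximum CTCAE Grade for post treatment lab assessments". Only the second has an exception to the scheduled-only rule: "The summary for the maximum CTCAE will be based on both scheduled and unscheduled visits".

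The SAP does not say whether the shift is to each visit or to the worst post-baseline grade. Neither SAP 12.2.1 nor Protocol 9.5.2 defines a treatment-emergent graded laboratory abnormality. Protocol 7.2.7 says that after an unexplained, clinically relevant abnormal result "the test should be repeated and followed up at the discretion of the investigator", and Protocol 7.1 allows unscheduled visits for safety reasons.

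**The concern.** One table has the baseline but not all the data. The other has all the data but not the baseline. The results left out of the shift tables are largely those taken because something already looked wrong.

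Other planned outputs only partly fill the gap. Laboratory results are a primary endpoint in every part (SAP 2.3.1). Under Protocol 8.1.1 and 8.1.3, an abnormality with no signs or symptoms and no need for intervention is not recorded as an AE, so it cannot reach the TEAE tables. Those tables apply a treatment-emergent rule; the graded laboratory tables have none.

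At stake is how far the tables alone let a reader separate new or worsened abnormalities from those present before dosing. An unexpanded Part B/C cohort has 3 active subjects, so one subject moves a percentage by 33 points.

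**Working it through.** **1. The two displays side by side** (SAP 12.2.1, read with SAP 3.1)

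| | Shift tables | Maximum-grade summary |
|---|---|---|
| Baseline grade shown | Yes | No |
| Worsening required | Not applicable: the shift itself is shown | No |
| Scheduled results | Yes | Yes |
| Unscheduled results | No exception stated; only re-tests replacing a missing scheduled value | Yes |

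**2. What a reader could recover.** Take five hypothetical subjects and one parameter, and give the shift table its most favourable layout (baseline to worst scheduled grade).

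| Subject | Baseline grade | Worst scheduled | Worst unscheduled | Shift table | Maximum-grade summary | Baseline to worst, all visits |
|---|---|---|---|---|---|---|
| 1 | 1 | 1 | none | 1 to 1 | 1 | 1 to 1 |
| 2 | 0 | 1 | none | 0 to 1 | 1 | 0 to 1 |
| 3 | 0 | 1 | 2 | 0 to 1 | 2 | 0 to 2 |
| 4 | 1 | 1 | 2 | 1 to 1 | 2 | 1 to 2 |
| 5 | 2 | 2 | none | 2 to 2 | 2 | 2 to 2 |

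The shift table shows 2 of 5 subjects worsening (subjects 2 and 3). Over all visits 3 of 5 worsened (2, 3 and 4), and subject 3 by two grades, not one. The maximum-grade summary shows three subjects at Grade 2 and cannot say that one of them (subject 5) started there. Only the last column, which no specified table contains, answers the question.

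**3. Can abnormalities be present at baseline?**
- Part B/C admits ALT and AST up to 2 x ULN (Protocol 5.4), and SAP 7.1.1 has a baseline category for ALT above ULN.
- Glucose, calcium, uric acid, ALP, GGT and LDH are measured (Protocol Table 6), but no part sets an entry limit on them (Protocol 5.2 to 5.5).
- Where limits exist they apply at screening, up to 28 days before Day 1. Baseline is the last valid pre-dose value (SAP 3.2), so a normal screening value does not guarantee a normal baseline.

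**4. Size.** The documents give no figure to reproduce and no baseline prevalence. Assume that a share p of subjects has a graded abnormality of a given parameter before dosing and that nothing changes afterwards. With 3 active subjects per unexpanded Part B/C cohort (Protocol 4.1.2), the chance that at least one is counted in the maximum-grade summary is 1 - (1 - p)^3:

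| p | 1 - (1 - p)^3 |
|---|---|
| 5% | 1 - 0.95^3 = 14% |
| 10% | 1 - 0.90^3 = 27% |
| 20% | 1 - 0.80^3 = 49% |
| 30% | 1 - 0.70^3 = 66% |

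At full Part B/C enrolment of 48 at 3:1 (36 active, 12 placebo), p = 10% to 30% gives 36p = 3.6 to 10.8 active and 12p = 1.2 to 3.6 placebo subjects counted without any change. A rule requiring a rise of at least one grade would count none of them.

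**The case against.** The strongest reply is that nothing is lost. A worst unscheduled grade does enter the maximum-grade summary. The listings hold every result, the derived grades and the flagged baseline record (SAP 12.2.1). With cohorts of 4 and no hypothesis testing (SAP 3.3), comparing by hand is practical. Summaries of values and changes from baseline by visit are also planned, Part B/C laboratory visits are weekly through Week 8, and abnormalities needing intervention are recorded as AEs. All of this stands and limits the harm. It does not supply a prespecified table for a primary endpoint.

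The reply can add that exclusion of unscheduled results from the shift tables follows from the general rule and is not stated for those tables, and that the table shells, which might settle the layout, are not in the public text. That is fair. But the SAP wrote an exception for one display and not for the other, and even a shift to the worst scheduled grade would leave out unscheduled results.

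Three stronger readings are tempting and are not supported:
- A reader might infer that the SAP classes pre-existing abnormalities as toxicity caused by treatment. It does not. The label is maximum grade after treatment, next to a shift table, so the risk is one of misreading.
- A reader might infer that entry criteria leave baseline laboratory values largely open. They do not. Haematology, creatinine, total bilirubin, albumin, sodium and potassium are restricted at screening in all parts, INR and prothrombin time in Part B/C, and ALT and AST in Part A.
- A reader might take chance imbalance as the size of the defect. Comparing 3 active with 3 placebo subjects, the counts differ with probability 41% at p = 10% and 65% at p = 30% (one minus the sum of squared binomial probabilities). Any event with that background rate behaves the same way, including new-onset events under a better rule, so the figure mostly reflects cohort size.

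**Conclusion.** The point holds as a gap in the specified tables. As SAP 12.2.1 is written, no summary table sets the worst post-baseline grade over scheduled and unscheduled visits against baseline, and the maximum-grade summary cannot distinguish an unchanged abnormality from a new one. No data are lost, and the listings allow the comparison, so the consequence is limited. It is still worth correcting, because the endpoint is primary and the inputs already exist.

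The 27% to 66% per parameter rests on an assumed baseline prevalence of 10% to 30%, persistence after dosing, 3 active subjects per cohort and independence between subjects. It also assumes that the grade depends on the value alone. The documents do not reproduce the CTCAE v5.0 criteria, so they do not show which tests are graded, or whether the grading of a test already allows for an abnormal baseline. Where it does, the second half of the problem shrinks for that test. The omission of unscheduled results from the shift tables remains. How often a worst value would occur only at an unscheduled draw cannot be estimated from the documents.

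**What to change.** In SAP 12.2.1:

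- Define the shift table, per parameter, as baseline grade against maximum post-baseline grade, using scheduled and unscheduled results through 12 weeks after the last dose, the summary window in Protocol 9.5.
- Report a graded abnormality as treatment-emergent only if the grade rises by at least 1 from baseline.
- State a rule for a missing baseline grade. Creatine kinase needs one: Protocol Table 6 requires it only when ALT or AST has risen to a stated multiple of the Day 1 value, so most subjects may have no pre-dose result.
- Say how the last visit is handled. A second dose on Day 29 plus 84 days gives Day 113, the nominal Week 16 visit, whose window is 7 days either way. A late visit should not drop out by accident.
- Keep the absolute maximum-grade summary alongside, labelled as not adjusted for baseline. List extended follow-up liver tests (Week 20 onward) separately, since only subjects with a sustained HBsAg fall contribute them.

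The cost is SAP wording, one changed table shell and slightly more programming. Grades and baseline flags are already derived for the listings. If visit-by-visit grade shifts are wanted, they can go in an extra table or stay in the listings.

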12.3 Vital Signs Measurements

The following vital signs measurements will be taken at the time points specified in the Schedule of Events (refer to the Protocol):

- Pulse Rate (beats/min)
- Systolic blood pressure (SBP) (mmHg)
- Diastolic blood pressure (DBP) (mmHg)

- Respiratory rate (breaths/min)
- Temperature (°C)

12.3.1 Biostatistical Methods

All vital signs data collected at scheduled and unscheduled visits will be included in the listings, but only results collected as scheduled visits will be included in the summary tables.

The parameter names that will be used in the outputs will comprise of the test name and the unit of measure, for example, 'Systolic Blood Pressure (mmHg)'. Parameters will be sorted in the order that the measurements were collected in on the Vital Signs eCRF page within the tables and listings.

The change from baseline to the pre-dose assessment at each post-baseline visit will be calculated for all parameters. If unscheduled assessments are recorded on Day 1, the average of the pre-dose Day 1 and unscheduled assessments will be used as baseline for all change from baseline calculations.

The decimal precision to which the summaries for each parameter will presented will be based on the maximum number of decimals to which the results were reported on the eCRF.

Vital signs measurements will present summary statistics for the results at the baseline and each scheduled post-baseline visit for each of the parameters. In addition, summaries will be presented for the change from baseline values at each scheduled post-baseline visit.

The listings of vital signs measurements will include all the information collected. In addition, the observations that are used as the baseline record (value) for each parameter will be flagged, and the change from baseline values at each post-baseline visit will be presented.

12.4 12-Lead Safety Electrocardiogram (ECG)

12-lead safety ECGs interpretations will be recorded and reviewed on-site by the investigator as outlined in the protocol scheduled of event in Appendix 2 and Appendix 3. Specified collection timepoints for each visit are provided in the protocol: Appendix 4 and Appendix 5.

Holter ECG analysis falls outside the scope of the study.

12.4.1 Biostatistical Methods

All ECG data collected at scheduled and unscheduled visits will be included in the listings, but only results collected as scheduled visits will be included in the summary tables.

The summary of overall interpretation findings table will present counts and percentages for the reported results at baseline and each post-baseline visit/time point. Result categories will be ordered as 'Normal', 'Abnormal Not Clinically Significant (NCS)' and 'Abnormal Clinically Significant (CS)'.

The listings of ECG measurements will include all the information collected data. In addition, the observations that are used as the baseline record (value) for each parameter will be flagged, and the change from baseline values at each post-baseline visit will be presented.

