7. STUDY PROCEDURES

7.1. Procedures and Specifications

The Schedule of Study Assessments is provided in Appendix 2 for Part A and Appendix 3 for Part B/C. Unscheduled visits are permitted at the discretion of the investigator as needed for safety assessment.

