Per Section 8.1.1, laboratory abnormalities without an associated AE (signs or symptoms) and/or which do not require medical intervention, are not themselves recorded as AEs or SAEs. However, laboratory abnormalities (eg, clinical chemistry, hematology, and urinalysis) that require medical or surgical intervention must be recorded as an AE, as well as an SAE, if applicable. In addition, laboratory or other abnormal assessments (eg, electrocardiogram, vital signs) that are associated with signs and/or symptoms must be recorded as an AE or SAE if they meet the definition of an AE or SAE as described in Sections 8.1.1 and 8.1.2. If the laboratory abnormality is part of a clinical syndrome, record the syndrome or diagnosis (eg, anemia), not the laboratory result (ie, decreased hemoglobin).

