9.5. Safety Analysis

All safety analyses will be performed using the Safety Analysis Set. Safety will be evaluated by assessment of clinical laboratory tests, physical examinations, ECGs, vital signs measurements at various timepoints during the study, and by the documentation of AEs.

All safety data collected up to 12 weeks after the last study drug administration will be summarized by cohort for each VIR-2218 dose and placebo.

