^g Vital signs (blood pressure, pulse rate, respiratory rate and temperature) should be measured after the subject has rested comfortably for approximately 10 minutes. On Day 1, vital signs should be measured within 2 hours predose and 4 hours post-dose. On all other visit days, vital signs are only required to be recorded once during the visit.

^h 12-lead safety ECGs will be recorded on the timepoints listed in Appendix 4 and should be measured in the supine position after the subject has rested comfortably for 10 minutes.

ⁱ Replicate 12-lead ECGs will be extracted at the central ECG laboratory at timepoints shown in Appendix 4. Subjects must be resting supine for at least 10 minutes prior to and 5 minutes after each nominal timepoint.

^j WOCBP are required to have pregnancy tests. A blood pregnancy test will be performed at screening and urine pregnancy tests will be performed thereafter. Negative pregnancy test must be confirmed prior to study drug administration.

^k See Section 7.1.3 for viral serology parameters.

^l Clinical laboratory and urinalysis parameters are described in Section 7.2.8.

^m Drugs of abuse included in the screen are described in the inclusion/exclusion criteria. Screening results for drugs of abuse must be reviewed prior to dosing.

ⁿ Study drug will be administered via SC injection as described in Section 6.2.4.

^o Blood and urine samples for PK analysis will be collected at the timepoints listed in Appendix 4.

^p All AEs related to screening activities must be collected from the time of consent onwards; any other events occurring during the screening period should be reported as medical history. All SAEs must be collected from the time of consent onwards.

Appendix 3. Part B/C Schedule of Study Assessments for MAD Cohorts in Subjects with Chronic HBV Infection

Part B/C																
Study Stage	Screening	Dosing Period						Post-dose Follow-up Period ^b						Extended Follow-up Period ^c		
Study Visit Week				W1	W2	W3	W4 ^a	W5	W6	W7	W8	W12	W16	W20	W24	
Study Visit Day ± Visit Window	D -28 to -1	D1 ^a	D2	D8 ±2	D15 ±2	D22 ±2	D29 ^a ±2	D36 ±2	D43 ±2	D50 ±2	D57 ±2	D85 ±7	D113 ±7/ET	D141 ±7	D169 ±7	Q28D ±7
Informed consent	X															
Demography	X															
Medical history including HBV genotype ^d	X															
Inclusion/exclusion criteria	X	X ^c														
Full physical examination ^f	X						X						X			
Symptom-directed physical examination		X	X	X	X	X		X	X	X	X	X				

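### ECG and vital-sign tables take scheduled results only, so post-baseline readings prompted by a safety concern reach the listings but no by-dose ECG or vital-sign table described in the SAP.

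*SAP*

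**What the plan says.** **ECG and vital signs.** SAP 12.4.1 puts all ECG data in the listings, but "only results collected as scheduled visits will be included in the summary tables". SAP 12.3.1 has the same rule: "All vital signs data collected at scheduled and unscheduled visits will be included in the listings, but only results collected as scheduled visits" go into the tables. The ECG table described is a by-visit count of Normal, Abnormal NCS and Abnormal CS. The vital-sign tables give by-visit values and changes from baseline.

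**Exceptions.** SAP 3.1 tabulates an unscheduled re-test that replaces a missing scheduled value. If a scheduled result exists and is repeated, the first result stands. SAP 3.2 lets unscheduled values enter baseline, and SAP 12.3.1 averages unscheduled Day 1 vital signs into it.

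**Laboratory data.** SAP 12.2.1 also keeps the by-visit tables to scheduled results, but adds a worst-value display: "The summary for the maximum CTCAE will be based on both scheduled and unscheduled visits". SAP 13.2 likewise uses unscheduled visits for the HBsAg nadir.

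**Protocol.** Section 7.1: "Unscheduled visits are permitted at the discretion of the investigator as needed for safety assessment". Section 9.5: "All safety data collected up to 12 weeks after the last study drug administration will be summarized by cohort for each VIR-2218 dose and placebo". Section 9.5.3 has ECGs and vital signs listed, and summarized either by incidence of abnormalities or by descriptive statistics, as appropriate. SAP 15 records no change to the planned analysis.

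**The concern.** Safety and tolerability are the primary objective in every part of the study. Unscheduled visits exist for safety assessment, so readings taken at them are more likely than routine ones to be abnormal. Under the table rule, those are the readings left out of the ECG and vital-sign summaries. The SAP avoids this for laboratory data by adding a maximum-grade table, and describes nothing similar for ECG or vital signs.

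At stake is a simple question that a dose-escalation report should answer: at each dose, how many subjects ever had a clinically significant ECG or an extreme vital sign after dosing? No described table answers it with the safety-prompted readings included.

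**Working it through.** The documents give no figure for ECG coverage, so there is none to reproduce. The check is how much of follow-up is open to each route into a table.

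**Inputs**
- Last scheduled safety ECG, Part A: Week 1, Day 8 ± 2 (Protocol Appendices 2 and 4). None at Weeks 2 to 12 or at early termination.
- Last scheduled safety ECG, Part B/C: Week 4, Day 29 ± 2, 4 hours after the second dose (Appendices 3 and 5). None at Weeks 5 to 16 or at early termination.
- End of follow-up: Day 85 ± 7 in Part A; Day 113 ± 7 in Part B/C. Both are 12 weeks after the last dose: 1 + 84 = 85 and 29 + 84 = 113.
- AE tables are restricted to TEAEs (SAP 12.1.2), and the TEAE window closes 30 days after the last dose (SAP 12.1.1): Day 1 + 30 = Day 31 in Part A, Day 29 + 30 = Day 59 in Part B/C.

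**Step 1: follow-up after the last scheduled ECG**

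Share = (end day − last ECG day) / (end day − 1)

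- Part A: (85 − 8)/84 = 77/84 = 91.7%. Across the visit windows: 88.3% to 94.5%.
- Part B/C to Week 16: (113 − 29)/112 = 84/112 = 75.0%. Across the windows: 71.4% to 78.2%.

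In these periods nothing can enter the ECG summary table.

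**Step 2: allow for the TEAE tables**

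An ECG abnormality recorded as an AE is counted by cohort in the TEAE tables until the window closes. This covers a further (31 − 8)/84 = 23/84 = 27.4% in Part A and (59 − 29)/112 = 30/112 = 26.8% in Part B/C. The share that neither route covers is:

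- Part A: (85 − 31)/84 = 54/84 = 64.3%.
- Part B/C: (113 − 59)/112 = 54/112 = 48.2%.

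For a subject followed to Week 48 (Day 337) the two shares become 308/336 = 91.7% and 278/336 = 82.7%. That extension lies beyond the 12 weeks named in Protocol 9.5, so the Week 16 figures are the relevant ones.

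**Step 3: what AE recording requires**

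Protocol 8.1.3 covers abnormal laboratory or other assessments, with ECG and vital signs as its examples: those "that are associated with signs and/or symptoms must be recorded as an AE or SAE" if they meet the AE or SAE definition. Recording is therefore mandatory for symptomatic findings. For asymptomatic ECG or vital-sign findings the text neither clearly requires nor excludes it.

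**Step 4: vital signs**

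These are scheduled at nearly every visit to Week 12 (Part A) or Week 16 (Part B/C), so the coverage shares above do not apply. The issue there is only the omitted unscheduled readings.

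A side note on wording: the Day 1 averaging sentence in SAP 12.3.1 does not limit the unscheduled readings to those before dosing, whereas the baseline definition in SAP 3.2 does.

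**The case against.** The case against is substantial, and much of it stands.

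- **A reader might infer that no ECG abnormality can reach any table for 92% or 75% of follow-up.** That is not so. The AE route stays open to Day 31 or Day 59, and the figures for both routes closed are 64% and 48%.
- **A reader might infer that an asymptomatic finding would appear in no count by dose.** The documents do not establish this. Protocol 8.1.3 does not say that only symptomatic findings are recorded. The AE definition in 8.1.1 is broad, and the exemptions for symptom-free abnormalities name laboratory results, not ECGs or vital signs. An investigator could record such a finding as an AE.
- **A reader might infer that the planned tables are biased downward, by 17 points for one subject in 6 or 33 points for one in 3.** By-visit tables describe scheduled visits and are valid for them. They do not claim to give per-subject incidence. Those steps also ignore floater subjects and the pooled VIR-2218 column.
- **A reader might see a breach of the protocol.** Section 9.5 is general. Section 9.5.3 is specific and leaves the form of summary open, so there is tension but no clear contradiction.
- **The coverage shares come from the ECG schedule combined with the table rule**, not from the rule alone. The documents give no rate of unscheduled ECGs, so the number of readings affected is unknown.
- **The consequence is limited.** All readings are listed by subject, planned cohorts are small, there is no hypothesis testing, and the Safety Review Committee reviews available data as the study runs.
- **The contents of SAP 18 are redacted**, so a worst-value display could exist there.

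What this leaves untouched is that SAP 12.3.1 and 12.4.1, which set out the methods, describe no per-subject, by-dose summary that includes the safety-prompted readings, while 12.2.1 does so for laboratory grades.

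**Conclusion.** The point holds as a cheap improvement, not as an error in the planned tables. Post-baseline ECG and vital-sign readings from unscheduled visits reach the listings but no by-dose ECG or vital-sign table described in the SAP, apart from re-tests that replace a missing scheduled value.

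For ECG only, the summary table is closed for 92% of follow-up in Part A and 75% in Part B/C to Week 16. Neither that table nor a TEAE table is open for 64% and 48%.

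These shares assume nominal visit days, the last scheduled ECG done on time, both doses given in Part B/C, and no undisclosed worst-value display in the redacted SAP 18. They measure time not covered. They do not estimate how many abnormalities would be missed.

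**What to change.** Keep the by-visit tables unchanged. Add to SAP 12.3.1 and 12.4.1 a worst post-baseline summary by cohort, for pooled VIR-2218 and for pooled placebo, using scheduled and unscheduled results up to 12 weeks after the last dose:

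- **ECG:** each subject's worst interpretation (Normal, Abnormal NCS, Abnormal CS), with a shift from baseline.
- **Vital signs:** each subject's post-baseline minimum and maximum for each parameter.

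Show the number of assessments per subject beside each summary, because subjects with more visits have more chances of a worst value.

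The cost is a few lines of SAP text and two tables from data already collected. No change to the ECG schedule is needed, and the approach follows what SAP 12.2.1 already does for maximum CTCAE grade.
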